### ***10.2.2      Replacement of Participants Who Withdraw from the Study***

Participants who withdraw from the study after receiving an initial dose of treatment will not be replaced. If a participant withdraws after randomization and before dosing, that participant may be replaced. The replacement participant will undergo the same stratification procedure as a new participant; no special replacement randomization schedule is necessary.

## **11 EVALUATION, RECORDING, AND REPORTING OF ADVERSE EVENTS**

### **11.1 Definitions**

#### ***11.1.1 Adverse Event***

An AE is any untoward medical occurrence or the deterioration of a pre-existing medical condition (other than the condition that is being treated by the study) associated with the use of a study medication in humans, whether or not it is considered related to the study medication. An AE (also referred to as an adverse experience) can therefore be any unfavorable and unintended sign (eg, tachycardia, enlarged liver, clinically important abnormal laboratory result or diagnostic procedure), participant-reported symptom (eg, nausea, chest pain), or evidence of any disease activity temporally associated with the use of a study medication, whether or not related to the study medication.

In clinical studies, an AE can include an undesirable medical condition occurring at any time after the participant has signed informed consent, including run-in or washout periods, even if no specific treatment has been administered.

Preexisting medical conditions (other than natural progression of the disease being studied) judged by the investigator or participant to have worsened in severity or frequency or changed in character during the protocol-specified AE reporting period will be reported as AEs or SAEs as appropriate.

Imaging-based assessments of a decrease in contractility are not considered AEs unless associated with symptoms or signs of clinical concern on the part of the investigator. Such events should be categorized as an AE defined in terms of those symptoms or signs.

An AE or SAE can also be a complication that occurs as a result of protocol-mandated procedures (eg, invasive procedures such as biopsies).

For MyoKardia to collect additional information about clinically important laboratory results or diagnostic tests (eg, blood, ECG, imaging), at a minimum, the following abnormalities should be captured on the AE eCRF:

- Any test result that meets the definition of an SAE (see [Section 11.1.2](#))
- Any clinically important test abnormality that suggests a disease and/or organ toxicity is worsening or is new (eg,  $> 3 \times$  deviation from the upper or lower limit of the analyzing laboratory reference range, or as otherwise specified in the protocol)
- Any test abnormality that requires the participant to have study medication discontinued or interrupted in the clinical judgment of the investigator

- Any test abnormality that requires the participant to receive specific corrective therapy, close observation, more frequent follow-up assessment, or further diagnostic investigation

The term AE is used generally to include any AE whether serious or nonserious.

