#### **7.5            *Guidelines for the Management of Exaggerated Pharmacologic Effect (Systolic Dysfunction), Higher Than Expected Plasma Concentration, or Excessive QT Prolongation***

If during the treatment period a participant has a resting LVEF  $\leq 45\%$ , plasma drug concentration  $\geq 1000 \text{ ng/mL}$ , or QTcF  $\geq 500 \text{ ms}$  (as determined by the echocardiography central laboratory, PK analysis laboratory, or ECG core laboratory, respectively), it will be communicated to the investigator and Sponsor that a stopping criterion has been met. Upon receipt of this information, the study site/investigator will contact the participant by

telephone and instruct the participant to discontinue study drug and return for the next scheduled onsite study visit or within 2 weeks, whichever is earlier. After the participant discontinues study drug, the participant will be encouraged to undergo early termination (ET) and EOS assessments (see [Section 10.1.4](#)). To maintain the study blind, a participant in either of the other 2 treatment groups may be randomly selected via the IXRS to similarly discontinue study drug.

If a participant experiences heart failure related to systolic dysfunction, no further study drug should be administered and administration of therapeutic doses of a  $\beta$ -adrenergic agonist (eg, 5 to 10  $\mu$ g/kg/min dobutamine infusion) should be considered. Additional supportive measures, eg, intravenous volume supplementation and/or the use of arterial vasoconstrictor agents ( $\alpha$ -adrenergic agonists) could complement the use of a  $\beta$ -adrenergic agonist. Aside from this specific advice regarding the role of a  $\beta$ -adrenergic agonist, appropriate care will be determined by the treating medical personnel.

New or worsening heart failure associated with systolic dysfunction is one of the criteria for permanent treatment discontinuation ([Section 10.1.3](#)) and should be subsequently managed as described in [Section 10.1.2](#) and [Section 10.1.4](#).

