## 8 RISKS AND PRECAUTIONS

### 8.1 General

Based on nonclinical data and the available clinical data, the most likely risks are those associated with higher exposures potentially resulting in an excessive decrease in LVEF. This could result in the development or worsening of signs or symptoms of systolic heart failure or reduced cardiac output.

Safety testing in other mammalian species has demonstrated that dose-limiting toxicity is related to exaggerated pharmacologic effect and not to off-target adverse effects. For overdose, see [Section 7.6](#).

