#### **11.2.1.3 Adverse Events of Special Interest**

Overdose, pregnancy, and LVEF  $\leq$  30% (as determined by local site—read echocardiogram) are considered adverse events of special interest (AESIs). Pregnancy includes the pregnancy of a female participant or the pregnancy of a partner of a male participant during the study up to 3 months after the last dose of study drug.

If an AESI occurs, this event must be reported to MyoKardia within 24 hours of knowledge of the event. A pregnancy will be followed until the final outcome, and a live birth will be followed for 6 months after the birth.

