6.1. Study Endpoints

Safety Endpoints:

- Frequency and severity of treatment-emergent AEs, AEs of special interest, and SAEs
- Frequency of laboratory abnormalities
- Change from baseline vital signs
- Frequency of cardiac rhythm abnormalities

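### The adverse event rules disagree on how to record an asymptomatic LVEF fall, so safety counts for the same event can differ between sites

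*Protocol*

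**What the plan says.** **AE definition.** Protocol 11.1.1 states: "Imaging-based assessments of a decrease in contractility are not considered AEs unless associated with symptoms or signs of clinical concern". Where such symptoms or signs exist, the event is to be recorded as those symptoms or signs.

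**AE form.** Later in the same section comes a minimum capture list. For "clinically important laboratory results or diagnostic tests (eg, blood, ECG, imaging), at a minimum, the following abnormalities should be captured on the AE eCRF". Two items matter here: "Any test abnormality that requires the participant to have study medication discontinued or interrupted in the clinical judgment of the investigator", and "Any test abnormality that requires the participant to receive specific corrective therapy, close observation, more frequent follow-up assessment, or further diagnostic investigation". Imaging is named, and contractility is not excepted.

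**AESIs.** Protocol 11.2.1.3 says that overdose, pregnancy and a site-read LVEF ≤ 30% "are considered adverse events of special interest (AESIs". It sets no symptom condition and asks for reporting within 24 hours.

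**Stops.** Under Protocol 7.5.1 a confirmed site reading of LVEF ≤ 30% is notified to the investigator and study drug is stopped. Under 7.5 a central-read LVEF ≤ 45% is one of three stopping criteria, with plasma concentration and QTcF; "it will be communicated to the investigator and Sponsor that a stopping criterion has been met". To protect the blind, participants in the other groups may be picked at random to stop as well. Protocol 6.2 keeps echo results from the site.

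**Outputs.** Protocol 8.1 says "the most likely risks are those associated with higher exposures potentially resulting in an excessive decrease in LVEF". The first safety endpoint in SAP 6.1 is "Frequency and severity of treatment-emergent AEs, AEs of special interest, and SAEs"; the others are laboratory abnormalities, vital signs and cardiac rhythm. SAP 13.1 plans tables of TEAEs, AESIs and TEAEs leading to permanent discontinuation. SAP 13.6 counts participants who met each stopping criterion.

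**The concern.** The only visible objective is safety and tolerability, and safety is analysed descriptively, so the counts are the result. If two sites can enter the same asymptomatic LVEF fall differently and both follow the protocol, the AE-based tables do not have one meaning. The events affected belong to the risk that the protocol itself ranks as most likely. Protocol 5.1 allows up to 35 sites for about 60 participants, so few sites will see enough cases to settle on a consistent practice.

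**Working it through.** The plan gives no figure to reproduce. The sample size is stated as about 20 per group without power inputs. The check is a comparison of the rules, then a scale.

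**Step 1. Apply each rule to the same two events, both without symptoms.**

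| Rule | Confirmed site-read LVEF ≤ 30% | Central-read LVEF ≤ 45% |
|---|---|---|
| Contractility sentence (11.1.1) | Not an AE | Not an AE |
| Capture list, drug stop (11.1.1) | Fits: the investigator knows the reading and drug is stopped | Not clearly triggered: the item rests on the investigator's judgment, the stop on a laboratory finding |
| Capture list, closer follow-up (11.1.1) | Can fit: an early termination visit follows (10.1.4) | Can fit: no judgment qualifier, and 7.5 calls the participant back at the next onsite visit or within 2 weeks |
| AESI rule (11.2.1.3) | AESI | Not an AESI |
| What the site knows | The reading | Only that a criterion was met; it could be any of three, and some stops are made for the blind |
| SAP 13.1 | AESI table, listed among the TEAE types | TEAE and discontinuation tables, only if an AE was entered |
| SAP 13.6 | Counted if it also meets the central criterion | Counted by arm |

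For ≤ 30% the rules give opposite answers. SAP 13.1 adds to this: it treats the AESI table as a kind of TEAE table but gives no route into it for an AESI that is not an AE. Pregnancy and overdose have their own summaries in Protocol 12.3.8.1 and their own outputs in SAP 13.1. LVEF ≤ 30% has neither.

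For ≤ 45% the conflict runs through the follow-up item only. Here the site lacks the information to apply any rule. Neither document says how true stops and blind-preserving stops enter the discontinuation table.

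**Step 2. Scale.** One case recorded or not moves incidence by 1/20 = 5.0 percentage points in one arm, and by 1/40 = 2.5 points in the two active arms together.

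With k asymptomatic cases, the AE-based row reads 0 under the contractility sentence and k under the capture list. The documents give no expected k. As an illustration only, take k = 3 of 20, with a range of 1 to 4, and exact (Clopper-Pearson) 95% intervals. For zero events the upper limit is 1 − 0.025^(1/20) = 16.8%.

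- Under exclusion: 0/20 = 0% (0 to 16.8%).
- Under capture: 3/20 = 15% (3.2 to 37.9%).
- Ends of the range under capture: 1/20 = 5% (0.1 to 24.9%) and 4/20 = 20% (5.7 to 43.7%).

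**Step 3. Would the conflict arise at all?** The chance of at least one case in n participants is 1 − (1 − p)^n. At assumed true rates p of 2%, 5%, 10% and 20% it is 33%, 64%, 88% and 99% for n = 20.

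**The case against.** The best defence is that the AESI category is deliberately wider than the AE category. Pregnancy is reportable even without an AE, and an overdose may be asymptomatic, so an AESI that is not an AE is no contradiction by itself. A specific sentence on contractility can also be read as overriding a generic list. And for ≤ 30% the investigator does know the result. This has force, but it does not close the gap. The protocol states no order of precedence, the capture list names imaging, and SAP 13.1 places AESIs inside the TEAE tables.

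On ≤ 45%, a reader might infer that one sentence forbids an AE entry and another demands it. The documents do not support that: the drug-stop item depends on the investigator's clinical judgment, and this stop is triggered centrally under blinding. Only the follow-up item remains in tension.

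A reader might also infer that the plan leaves the main risk unmeasured. That does not follow either. AESIs are a listed safety endpoint and include LVEF ≤ 30%. SAP 13.6 counts the ≤ 45% criterion by arm, and SAP 7 reports reasons for discontinuation. The non-safety sections are blacked out, and the SAP's visit windows match the post-baseline resting echo visits, so LVEF by visit may be summarised there. Nor does the visible text designate the TEAE tables as a primary endpoint.

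Finally, no test or decision rule changes, because the safety analysis is descriptive.

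**Conclusion.** The inconsistency is real and should be corrected. It is direct for a confirmed, asymptomatic site-read LVEF ≤ 30% and weaker for a central-read LVEF ≤ 45%, where blinding and blind-preserving stops are the larger difficulty. TEAE, AESI and TEAE-leading-to-discontinuation counts can differ with the site's reading of the rules, by 5 percentage points per case in an arm of 20. How many cases would be affected is unknown; the illustration of 3 in 20 is an assumption, and the arithmetic assumes that all 20 in the arm are dosed.

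On LVEF itself the conclusion is narrow. It is not listed separately among the visible safety endpoints, and SAP section 13 shows no summary of LVEF change or of falls that stay above 45%. Absence from the whole plan cannot be claimed.

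**What to change.** **1. Reconcile the recording rules** in Protocol 7.5, 11.1.1 and 11.2.1.3, so that an LVEF finding that meets an existing AESI or stopping threshold is recorded in one stated way, with or without symptoms. Then, in SAP 13.1:

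- derive the ≤ 30% AESI count from the confirmed site echo record;
- derive the ≤ 45% count from central-laboratory echo data, not from the IXRS stop record, which also holds the blind-preserving stops;
- state how true and blind-preserving stops are coded in the discontinuation table.

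Deriving these counts from the echo data at analysis leaves the sites blinded.

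**2. Make LVEF visible in the safety analysis.** In SAP 6.1 and 13, add central-read resting LVEF on the Safety population: change from baseline by visit, and number and percent ≤ 45% and ≤ 30% by arm. If a blacked-out section already has this, a cross-reference is enough. Label the central-read ≤ 30% count apart from the site-read AESI count, since the two may differ.

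**Cost.** Wording changes and one or two extra descriptive tables. Resting echo is already scheduled at Screening, Day 1 and Weeks 4, 8, 12, 16 and 24. No dose, threshold or stopping rule changes.

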#### 11.1.1.1 Events That Do Not Meet the Definition of Adverse Event

Events that do not meet the definition of AE include the following:

- Any clinically significant abnormal laboratory findings or other abnormal safety assessments which are associated with the underlying disease, unless judged by the investigator to be more severe than expected for the participant's condition
- The disease/disorder being studied or expected progression, signs, or symptoms of the disease/disorder being studied, unless more severe than expected for the participant's condition
- Medical or surgical procedure (eg, endoscopy, appendectomy, device implantation): the condition that leads to the procedure is the AE
- Situations in which an untoward medical occurrence did not occur (social and/or convenience admission to a hospital)
- Anticipated day-to-day fluctuations of preexisting disease(s) or condition(s) present or detected at the start of the study that do not worsen

#### 11.1.2 *Serious Adverse Event*

An SAE is an AE that fulfills one or more of the following criteria in the opinion of the investigator or MyoKardia:

- Results in death
- Is immediately life-threatening (places the participant at immediate risk of death from the event as it occurred)
- Requires in-participant hospitalization or prolongation of existing hospitalization
- Results in persistent or significant disability or incapacity or substantial disruption of the ability to conduct normal life functions
- Results in a congenital abnormality or birth defect
- Is an important medical event that may not result in death, be life-threatening, or require hospitalization, but may be considered an SAE when, based upon appropriate medical

judgment, it may require medical or surgical intervention to prevent one of the outcomes listed above

## **11.2 Adverse Event Reporting and Descriptions**

### ***11.2.1 Reporting Period and Follow-up***

#### **11.2.1.1 Adverse Events**

AEs will be assessed from the time the participant provides informed consent through the duration of the study. Preexisting medical conditions that increase in severity from the first dose of study medication will be reported as AEs. Preexisting medical conditions that increase in severity after providing informed consent but before the first dose of study medication will be reported as medical history.

Any AEs that are unresolved at the participant's last visit in the study will be followed by the investigator until resolved or stabilized and are considered irreversible, or the participant has died.

MyoKardia retains the right to request additional information for any participant with ongoing AE(s)/SAE(s) at the end of the study, if judged necessary.

#### **11.2.1.2 Serious Adverse Events**

All SAEs occurring during the treatment-emergent period (defined as the period from the first administration of study drug to 56 days [8 weeks] after the last administration of study drug) regardless of causality will be reported by the investigator or designee to MyoKardia or its designee within 24 hours of knowledge of the event. All follow-up information for previously reported SAEs will also be reported to MyoKardia or its designee within 24 hours of knowledge. SAEs occurring after informed consent is signed but before the first dose of study drug is administered will be reported as SAEs only if they are considered related to the protocol or study procedure.

SAE reporting instructions are provided in the Study Reference Manual.

#### **11.2.1.3 Adverse Events of Special Interest**

Overdose, pregnancy, and LVEF  $\leq$  30% (as determined by local site—read echocardiogram) are considered adverse events of special interest (AESIs). Pregnancy includes the pregnancy of a female participant or the pregnancy of a partner of a male participant during the study up to 3 months after the last dose of study drug.

If an AESI occurs, this event must be reported to MyoKardia within 24 hours of knowledge of the event. A pregnancy will be followed until the final outcome, and a live birth will be followed for 6 months after the birth.

## **11.2.2 Recording and Assessing Adverse Events**

### **11.2.2.1 Description**

All AEs spontaneously reported by the participant or reported in response to the open question from the study personnel “Have you had any health problems since you were last asked?”, or revealed by observation will be collected and recorded in the eCRF.

When collecting AEs the recording of diagnoses is preferred (when possible) to recording a list of signs and symptoms (eg, anemia, not low hemoglobin). However, if a diagnosis is known and there are other signs or symptoms that are not generally part of the diagnosis, the diagnosis and each sign or symptom will be recorded separately.

Death is an outcome and not the name of the event. In this situation, the event that led to the death is the name of the event. If the cause of death is unknown, “found dead” is an acceptable description.

### **11.2.2.2 Relationship to Study Treatment**

The investigator should assess causality by answering either “yes” or “no” to the question “Is there a reasonable possibility that the event may have been caused by the investigational medicinal product [IMP]/study medication?”

The following factors can be used in consideration of causality assessment:

- Challenge/rechallenge: Did the event abate after study medication was reduced or interrupted? Did the event reappear after study medication was reintroduced?
- Temporal relationship and time to onset plausibility
- Confounding risk factors
- Amount and duration of study drug exposure
- Concomitant medications

### **11.2.2.3 Severity**

Severity can be assessed as follows:

- Mild (awareness of sign or symptom, but easily tolerated)
- Moderate (discomfort sufficient to cause interference with normal activities)
- Severe (incapacitating, with inability to perform normal activities)
- Life-threatening (urgent intervention indicated)

- Fatal (event led to death)

**It is important to distinguish between category (AE vs SAE) and intensity (mild, moderate, or severe) of AEs.**

Severity is a measure of intensity, whereas seriousness is defined by the criteria in [Section 11.1.2](#).

An AE of severe intensity need not necessarily be considered serious. For example, nausea that persists for several hours may be considered severe nausea but not an SAE. On the other hand, a stroke that results in only a limited degree of disability may be considered a mild stroke but would be an SAE.

### **11.3 Suspected Unexpected Serious Adverse Reactions (SUSARs)**

SUSARs are SAEs that qualify for mandatory expedited reporting to regulatory authorities where the SAE is suspected to be caused by the study treatment and is considered unexpected (ie, not defined as expected in the current IB, clinical protocol, or approved labeling for marketed products). In this case, MyoKardia or its designee may be required per regulatory requirements to unblind the participant to determine treatment assignment. Only specified MyoKardia pharmacovigilance staff members or designees will have access to the unblinded information in order to meet regulatory requirements and report to the relevant regulatory authority(ies). A blinded report describing the SUSAR will be sent to all investigators. Each investigator must then notify his/her ethic committee (EC) of the blinded SUSAR as required by local regulatory authorities and in accordance with their EC policy.

## 12 STATISTICAL METHODS

### 12.1 Determination of Sample Size

This study will include a total of approximately 60 participants, or approximately 20 participants per treatment group. Such a sample size will be sufficient to obtain sound variability estimates while yielding reasonable effect size estimates for future planning purposes.

### 12.2 Study Endpoints

#### 12.2.1 *Safety Endpoints*

- Frequency and severity of treatment-emergent AEs, AESIs, and SAEs; laboratory abnormalities; vital signs; and cardiac rhythm abnormalities

## 12.3 Statistical Analysis

Before database lock, final SAPs for clinical data and PK data will be prepared that contain full details of all planned analyses. The analyses presented here represent an outline of the intended methodology.

### 12.3.1 *Analysis Populations*

Four analysis populations are defined in this study:

- Intention-to-treat (ITT) Population: all randomized participants regardless of whether they receive study drug, with analyses conducted according to the randomized treatment assignment
- Safety Analysis Population: all randomized participants who receive at least 1 dose of study drug, with analyses conducted by actual treatment received
- PK Analysis Population: all randomized participants who receive at least 1 dose of study drug and have at least 1 evaluable mavacamten plasma drug concentration
- PK/PD Analysis Population: all randomized participants who receive at least 1 dose of study drug, have at least 1 evaluable mavacamten plasma drug concentration, and have post-Baseline PD data; at least one 1 post-baseline PD data point must coincide temporally with an evaluable mavacamten plasma drug concentration

